3.4 Protocol deviations

Important protocol deviations are defined as those deviations from the protocol likely to have a meaningful impact on study conduct, or on the safety or efficacy outcomes for an individual

subject. The criteria for identifying important protocol deviations will be defined within the appropriate protocol-specific document. All potential protocol deviations will be reviewed as part of the ongoing data cleaning process and documented prior to database lock.

All deviations will be identified and classified as important or not important. Important protocol deviations will be identified and classified by the deviation types:

- Inclusion criteria deviation
- Exclusion criteria deviation
- Withdrawal criteria deviation
- Prohibited concomitant medication use
- Incorrect treatment or dose
- Treatment non-compliance
- Procedural non-compliance

The process for identifying and categorizing prohibited medications is described in [Section 6.5](#).

The impact of the Coronavirus Disease 2019 (COVID-19) pandemic on study procedures/conduct (eg, missed visits, remote visits, interruption of study treatment) will be documented using the information collected on a dedicated eCRF page the details for which are included in [Section 12.5](#). All data reported on this eCRF page will be reviewed during ongoing data cleaning meetings in order to determine if these should be considered as important protocol deviations.

3.5 Mapping of assessments

Study assessments at an Early Termination (ET) visit where the visit date is within the protocol-defined visit window of a scheduled site visit will be mapped to that scheduled site visit (this does not include home visits). Visit windows will be calculated relative to the date of first dose in AS0009 (planned at the AS0009 EV), but if the dose was missed at that visit, the date of the AS0009 EV will be used instead. The following rules will also be applied:

- If there is an existing scheduled site visit in the window, and the specific assessment was performed at that scheduled site visit, then the relevant assessments at the ET visit will be mapped to the next scheduled site visit (regardless of whether this is within the protocol-defined visit window for that site visit).
- Study assessments at an ET visit that does not fall into the protocol-defined visit window of a scheduled site visit will be assigned to the next scheduled site visit after the date of the ET visit (regardless of whether this is within the protocol-defined visit window for that site visit).
- Mapping of an assessment to a scheduled visit will occur regardless of whether the assessment was planned to be conducted at that visit (with the exception of ADAb). For ADAb however, data will only be mapped to scheduled site visits where ADAb levels are planned to be measured. Any PK samples taken at the same ET visit will be mapped to the same scheduled visit as the ADAb.

- Additional rules regarding visit mapping are provided in [Section 8.1.5](#) for BASMI and [Section 9.1](#) and [Section 9.2](#) for PK and ADA_b summaries respectively.

Unscheduled assessments where the visit date is within the protocol-defined visit window of a scheduled site visit will be mapped to that scheduled site visit (this does not include home visits). Visit windows will be calculated relative to the date of first dose in AS0009. But if the dose was missed at that visit, the date of the AS0009 EV will be used instead. The following rules will also be applied:

- If there is an existing assessment with a non-missing response (from a scheduled site visit or ET visit) in the window, the assessment will be left as unscheduled.
- Unscheduled assessments which do not fall within a protocol-defined visit window based on time since first dose (or date of AS0009 EV if the first dose was missed) will be left as unscheduled.
- Unscheduled assessments obtained at specific time points (e.g., vital signs) will only be mapped to a scheduled site visit for the equivalent time point. Thus, if an assessment falls within the protocol-defined visit window of a scheduled site visit but the scheduled visit does not have a corresponding time point, the measurement will be left as unscheduled (e.g., if the unscheduled time point was ‘1 HOUR POST DOSE’ this will not be mapped to a visit at which only ‘PRE DOSE’ time points are scheduled).
- Unscheduled PK and ADA_b assessments may also be mapped to a scheduled site visit if the visit date is within the protocol-defined visit window of that visit. For ADA_b this will only apply to scheduled site visits where ADA_b levels are planned to be measured. For any PK samples obtained at the same unscheduled visit, these will be mapped to the same scheduled visit as the ADA_b.

If there are multiple unscheduled assessments in a specific visit window, the first non-missing assessment will be mapped to the scheduled visit and used for summary statistics or frequency counts. Similarly, if there are multiple scheduled assessments performed on the same visit date, the first non-missing assessment will be used for summary statistics or frequency counts.

Assessments will be reported according to the planned Schedule of Assessments ([Table 2–1](#)) and each scheduled visit summary will include actual data and any data mapped from an ET visit to that scheduled visit. The final visit will be labeled “Week 208”. Data obtained at scheduled visits will be reported as per the database (i.e., these will not be remapped as described above).

Assessments mapped to visits at which the assessment was not planned, unscheduled visits and unscheduled assessments which are not mapped to scheduled visit at which the assessment was planned will be listed only.

3.6 Analysis sets

Three analysis sets will be defined for this study.

3.6.1 Enrolled Set

The Enrolled Set (ES) will consist of all subjects who have given informed consent for AS0009.

3.6.2 Safety Set

The Safety Set (SS) will consist of all subjects in the ES who received at least one dose of study medication in AS0009.

All safety variables will be summarized for the SS. Pharmacokinetic and immunological variables will also be summarized on the SS.

Two sub-populations of the SS will be defined for this study: Sub-population 1 will consist of all subjects in the SS who took no concomitant rescue medication in AS0009, and Sub-population 2 will consist of all subjects in the SS who took concomitant rescue medication in AS0009, as outlined in [Section 6.5](#). Rescue medications will be identified in the study database using the flag collected in the electronic case report form (eCRF). Concomitant medications are defined in [Section 6.4](#).

Selected summaries of the primary and secondary safety variables will be repeated for both SS Sub-populations only in the event that the number of subjects receiving rescue medication is $\geq 10\%$ of the total number of subjects in the SS.

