3 STUDY OBJECTIVES

3.1 Primary objective

The primary objective of this open-label study is to assess the long-term safety and tolerability of bimekizumab administered over a period of up to 204 weeks (~4 years).

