6.4 Past, prior and concomitant medications

Only medications that were ongoing at the end of AS0008 or were started during AS0009 will be reported.

Concomitant medications are medications taken at least 1 day in common with the study medication dosing period in AS0009 (as defined in [Section 3.2.2](#)). A medication is classed as concomitant if the start date is no later than the end date of study medication in AS0009 + 28 days, and the stop date is either missing or on or after the start date of study medication in AS0009. This includes medications that started prior to dosing in AS0009 and continued after.

For the purposes of the analysis, past medications are medications that started and stopped prior to dosing in AS0008. These include past TNF therapy (for subgroup analyses, MI modelling and baseline characteristics) and past NSAID therapy (for Baseline characteristics).

Missing or partial medication start and stop dates will be imputed as described in [Section 4.2.3](#). Imputations of missing data will be performed before calculation of relative study days and classification as concomitant.

The number and percentage of subjects taking concomitant medications will be summarized by ATC class, presenting Anatomical Main Group (ATC Level 1), Pharmacological Subgroup (ATC level 3), and PT, by treatment group at completion of AS0008 and overall for the SS.

All medications reported in AS0009, including flags to identify concomitant and rescue medications, and start and stop days relative to the start date of study medication in AS0008 and start and stop days relative to the start of study medication in AS0009, will be listed for the ES.

A glossary of all medications including the Anatomical Main Group (ATC Level 1), Pharmacological Subgroup (ATC level 3) PT and reported term will also be presented, based on the ES.

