6.5 Prohibited medication and rescue therapy

The following medication categories will be identified:

- Rescue medications as defined below. Subjects in the category ‘Any concomitant rescue therapy in AS0009’ will be considered SS Sub-population 2 and other subjects will be considered SS Sub-population 1. Rescue medications will be identified using the flag collected in the eCRF.
- NSAIDs to identify subgroups/covariates.
- Prohibited medications.

Rescue medications and NSAIDs will be classified into subcategories for reporting purposes. The identification and classification of concomitant medications will be performed by merging an external physician-reviewed spreadsheet (which includes relevant flags for selecting medications in each category) with the data entered into the study database in order to categorize the medications correctly for the tables.

The number and percentage of subjects who receive the following categories of rescue medication will be summarized by treatment group at completion of AS0008 and overall for the SS.

- Any rescue medication in AS0009 that is classified as a concomitant medication as defined in [Section 6.4](#).
- NSAID at AS0009 EV
- No NSAID at AS0009 EV
 - No NSAID at AS0009 EV and initiate NSAID [but not Cox-2 inhibitors] in AS0009 (only the initiation of NSAIDs that are classified as concomitant medications as defined in [Section 6.4](#) will be included).
 - No NSAID at AS0009 EV and initiate Cox-2 inhibitors in AS0009 (only the initiation of Cox-2 inhibitors that are classified as concomitant medications as defined in [Section 6.4](#) will be included).
- Use of any DMARDs in AS0009 alone or in combination (includes MTX, sulfasalazine, leflunomide and hydroxychloroquine). Only concomitant medications will be included as defined in [Section 6.4](#).
- Intra-articular corticosteroid in AS0009 that is classified as concomitant as defined in [Section 6.4](#).
- Oral corticosteroid in AS0009 that is classified as concomitant as defined in [Section 6.4](#).

- Analgesics in AS0009 that are classified as concomitant as defined in [Section 6.4](#).

Rescue therapy category and medication name, start date and day relative to start of study medication in AS0008 and AS0009 will be listed for the SS.

PRN analgesic and PRN opioid analgesic use within 24 hours prior to study visits will be listed for the ES, based on the dedicated eCRF page for prohibited medications.

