In the event that a subject received an incorrect (unplanned) treatment sequence the calculations for study medication duration and exposure time at risk will be adjusted accordingly following the principles outlined above and this will be documented in the relevant dataset specifications.

Three summaries of exposure will be provided: two for exposure in AS0009 and one for exposure in AS0008 and AS0009 combined.

- For the AS0009 summary, durations of exposure and times at risk will be summarized by treatment group at completion of AS0008 and overall. This summary will be repeated by SS Sub-population.
- For the AS0008 and AS0009 combined table, the duration of exposure and time at risk for 'BKZ 160mg', 'BKZ 320mg' and 'BKZ Total' will be summarized. Subjects who took bimekizumab 320mg during AS0008 will contribute to all three columns. Subjects who did not take bimekizumab 320mg in AS0008 will contribute to the 'BKZ 160mg' and 'BKZ Total' columns.

The total study medication duration and total time at risk will be included in the exposure tables. These will be calculated by summing the study medication duration (or time at risk) across all subjects (per treatment group) and will be expressed in years and presented to 1 decimal place.

Start date of study medication in AS0008, start and end dates of study medication in AS0009, the durations of exposure and the times at risk will be listed.

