- Serious TEAEs by treatment group at completion of AS0008 and overall, by SS Sub-population.
- All TEAEs in AS0008 and AS0009 by treatment at time of AE onset (BKZ 160mg, BKZ 320mg and BKZ Total).
- Serious TEAEs in AS0008 and AS0009 by treatment at time of AE onset (BKZ 160mg, BKZ 320mg and BKZ Total).

- All TEAEs AS0008 and AS0009 by timing of onset relative to ADAb status in AS0008 and AS0009. This will include columns for the following:
 - TEAEs starting before the first ADAb positive result in AS0008 and AS0009 (includes ADAb Categories 2b only)
 - TEAEs starting on the same date or after the first ADAb positive result in AS0008 and AS0009 (includes ADAb Categories 2b, 3b, 4b, 5b and 6b)
 - TEAEs for subjects who are ADAb negative at all time points in AS0008 and AS0009 (includes ADAb Categories 1b only)

Note that any TEAEs occurring for a subject who was ADAb positive at AS0008 Baseline will therefore all occur after ADAb positivity; such subjects will be excluded from the first column in the above table. Subjects in Category 9b (missing) will not be included in the table.

The following categories of TEAE will be summarized by MedDRA SOC, HLT and PT, by treatment group at completion of AS0008 and overall:

- TEAEs leading to study discontinuation and/or permanent withdrawal of study medication.
- TEAEs leading to permanent withdrawal of study medication.
- TEAEs with a fatal outcome.
- All TEAEs by maximum relationship.
- Serious TEAEs by maximum relationship.
- TEAEs with a fatal outcome by maximum relationship.
- All TEAEs by maximum intensity.
- Non-serious TEAEs reported by more than the reporting threshold of 5% of subjects. The cut-off will be applied before rounding on each treatment group and overall.

A further summary will be presented by treatment group at completion of AS0008 and overall displaying the frequency of TEAEs by descending frequency of PT.

An additional table will be presented by MedDRA SOC, HLT and PT, by treatment at time of AE onset (BKZ 160mg, BKZ 320mg and BKZ Total) for all TEAEs in AS0009 and all TEAEs that were ongoing from AS0008 at the time of the AS0009 EV. Ongoing TEAEs are defined as TEAEs that started prior to the AS0009 EV and continued after the first dose of study medication in AS0009.

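### The rescue sub-population tables label subjects by any rescue use in AS0009 but count from the first dose, so events and time before rescue are reported under rescue

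*SAP*

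**What the plan says.** SAP 3.6.2 defines the two groups at subject level. For the rescue group the rule is "Sub-population 2 will consist of all subjects in the SS who took concomitant rescue medication in AS0009"; those with no such use form Sub-population 1. SAP 6.5 applies the same rule: subjects with any concomitant rescue therapy "will be considered SS Sub-population 2 and other subjects will be considered SS Sub-population 1". Neither section sets a condition on when rescue began.

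The window is long. Protocol 3.1 has bimekizumab "administered over a period of up to 204 weeks (~4 years"), and SAP 6.4 counts a medication as concomitant if "the start date is no later than the end date of study medication in AS0009 + 28 days" and it had not stopped before the first AS0009 dose.

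Four outputs are repeated by this label. On exposure, SAP 10.1 says "This summary will be repeated by SS Sub-population". SAP 10.2 does the same for the TEAE overview, for all TEAEs, and for "Serious TEAEs by treatment group at completion of AS0008 and overall, by SS Sub-population". The last two carry EAIR and EAER. For tables of AS0009 events alone, SAP 10.2.2 starts time at risk at the first AS0009 dose. SAP 3.6.2 and 3.10 make the sub-population summaries conditional on at least 10% of the Safety Set receiving rescue.

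Protocol 13.2 also groups subjects by whether they receive rescue at all. No section of either document assigns a TEAE, or time at risk, by the date rescue began. SAP 6.5 lists those dates but uses them in no adverse event table.

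**The concern.** Membership depends on something that happens after entry, but it is applied back to the first dose. A subject rescued late brings all earlier rescue-free time, and every event in it, into the rescue column. A subject must also stay on study to be rescued, so those who leave early tend to fall into Sub-population 1. This is the familiar immortal-time problem.

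Protocol 13.2 asks for the primary and secondary variables in both groups, and SAP 10 treats the repeated tables as key safety analyses. Readers will naturally take the two columns as bimekizumab without and with added rescue therapy. Columns built this way do not show that. They are also produced only when rescue is reasonably common, which is when the misplacement matters.

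**Working it through.** The plan states no event rate, rescue rate or effect for this comparison, so there is no figure of its own to reproduce. Every rate below is an assumption.

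**Inputs from the documents.** Treatment lasts up to 204 weeks, followed by 20 weeks (140 days) at risk, so a completer has about 204 + 20 = 224 weeks. The 10% trigger with 285 subjects is 28.5, that is 29 subjects.

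**One subject.** First rescue at Week 190 puts 190/224 = 85% of that subject's time at risk into the rescue column although it preceded rescue.

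**Event rate (EAER).** Assume 100 events per 100 patient-years without rescue and 150 with it. If a fraction f of the time precedes rescue, Sub-population 2 shows f × 100 + (1 − f) × 150:

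- f = 0.25: 137.5, hiding 25% of the difference
- f = 0.50: 125, hiding 50%
- f = 0.75: 112.5, hiding 75%

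**Rate ratio for a completer.** With true ratio RR and w = week of first rescue / 224, the apparent ratio is w + (1 − w) × RR. For RR = 2:

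| First rescue | w | Apparent ratio |
|---|---|---|
| Week 24 | 0.107 | 1.89 |
| Week 48 | 0.214 | 1.79 |
| Week 102 | 0.455 | 1.54 |
| Week 200 | 0.893 | 1.11 |

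**Selection as well as misplacement.** The formulas above ignore who gets the chance to be rescued. A simulation of 400,000 subjects per scenario adds this. It assumes a first-event rate of 5 and a dropout rate of 8 per 100 patient-years, with rescue starting at 5, 15 or 40 per 100 patient-years. Rescue timing is unrelated to event risk except through the stated ratio. The event either never or always ends treatment. Ratios are Sub-population 2 over Sub-population 1. The last column splits events and time at the rescue start.

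| Rescue rate | True ratio | Event ends treatment | Pre-rescue share of Sub-population 2 time | EAIR ratio | Crude % ratio | EAIR ratio after split |
|---|---|---|---|---|---|---|
| 5 | 1 | no | 46% | 0.99 | 1.09 | 0.97 |
| 15 | 1 | no | 44% | 1.00 | 1.14 | 1.00 |
| 40 | 1 | no | 37% | 1.00 | 1.29 | 0.99 |
| 5 | 2 | no | 48% | 1.52 | 1.61 | 1.99 |
| 15 | 2 | no | 45% | 1.55 | 1.70 | 2.00 |
| 40 | 2 | no | 38% | 1.61 | 1.99 | 2.01 |
| 5 | 1 | yes | 45% | 0.52 | 0.62 | 1.01 |
| 15 | 1 | yes | 42% | 0.47 | 0.58 | 1.01 |
| 40 | 1 | yes | 35% | 0.34 | 0.49 | 1.00 |
| 5 | 2 | yes | 47% | 1.00 | 1.13 | 2.00 |
| 15 | 2 | yes | 44% | 0.88 | 1.06 | 1.99 |
| 40 | 2 | yes | 37% | 0.63 | 0.89 | 1.98 |

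Three patterns follow. With no rescue effect and follow-up unrelated to events, the EAIR ratio is close to 1, but the crude percentage is still 1.09 to 1.29 times higher in Sub-population 2. A true ratio of 2 is attenuated. When the event ends treatment, the comparison can reverse.

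**The case against.** The strongest reply is that the SAP follows the protocol's own ever/never grouping, that no objective compares bimekizumab alone with bimekizumab plus rescue, and that the tables are descriptive and conditional. All of that is true and limits the weight of the point. It does not change what the columns contain or how they will be read.

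Several stronger readings are tempting, and the documents do not support them.

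- A reader might infer that neither column shows bimekizumab without rescue. Sub-population 1 took no flagged concomitant rescue in AS0009, so all its time is rescue-free. Its fault is selection, not contamination.
- A reader might infer that the primary safety results are compromised. They are reported on the whole Safety Set, which the labels do not touch.
- A reader might infer that the grouping always dilutes a rescue effect. It can attenuate, leave the EAIR ratio near 1, or reverse it.
- A reader might take the 28-day allowance as an error in itself. It is the dosing interval that SAP 3.2.2 uses to end the dosing period. The difficulty is only that a late start relabels all earlier time.

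Two cautions about the remedy also stand. Rescue is given at the investigator's discretion for uncontrolled symptoms, so confounding by indication remains under any split. Also, an on-or-after-first-rescue column keeps counting after rescue stops. Protocol 7.8.1 permits steroid tapers of at most 14 days and single joint injections, so a brief early course would place most of a subject's time there.

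**Conclusion.** The point holds for the four sub-population outputs. Events and person-time before first rescue are reported under rescue, Sub-population 1 is selected on future follow-up, and no other section corrects either. Crude percentages, EAIR and EAER can be biased in either direction if read as safety without versus with rescue.

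The size in this trial is unknown. Under the assumed rates, 35% to 48% of Sub-population 2 time preceded rescue, and a true ratio of 2 appeared as an EAIR ratio of 1.52 to 1.61 when events did not affect follow-up. The ranges of 0.34 to 0.52 (true ratio 1) and 0.63 to 1.00 (true ratio 2) rest on the extreme assumption that the event always ends treatment. Subjects already on flagged rescue at the first AS0009 dose have no earlier AS0009 time to misplace, so the effect shrinks as their share grows.

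It would go too far to call the safety evidence unreadable. The whole Safety Set results stand, the affected tables are descriptive and appear only above the 10% trigger, and rescue start dates are already listed. The change is still worth making: the tables are planned, likely to be misread, and can be corrected from data already collected.

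**What to change.** For the exposure, TEAE overview, TEAE and serious TEAE tables, keep the 10% trigger and replace the ever/never columns as follows.

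1. Split each subject's events and time at risk at the start date of the first flagged rescue medication, imputed under SAP 4.2.3 if partial. Name the columns 'before or without rescue' and 'on or after first rescue'.
2. Start the clock for each column at the start of that segment. For EAIR, count the first occurrence within each segment. Base percentages on subjects at risk in that segment.
3. Rescue first started after the last bimekizumab dose then affects only time after its start.
4. Keep the protocol's ever/never membership for disposition counts, or as a footnoted companion table.
5. State that the second column includes time after rescue stops, and that the comparison is descriptive and confounded by indication. Record the change in SAP 3.10.

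The method is already in the SAP: 10.2.4 divides each subject's time at risk across COVID-19 periods and counts a subject in every period that applies, and 10.2 divides TEAEs at the first ADAb-positive result. No new data are needed; the work is wording and derivation.

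The costs are modest. Rescued subjects can appear in both columns. Partial medication dates blur some split points, by months where only the year is known. SAP 4.3 planned all but the COVID-19 outputs for the Week 108 interim, so the new tables will not match any interim versions unless the ever/never table is retained.
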